12.1.2 Secondary Objectives

A secondary objective of the study is the evaluation of the PD effect of VX-659 in TC with TEZ and either IVA or VX-561.

The absolute change from baseline through the Day 29 Visit in sweat chloride concentrations is a secondary endpoint used to evaluate the PD objective of the study. In Part 1, a test for a decreasing dose-response trend between placebo and the TC dose groups will be performed using a multiple comparisons procedure (MCP). The procedure consists of testing the null hypothesis of the lack of a decreasing dose-response trend versus a decreasing trend using the 1-sided maximum t -statistic that controls the type I error at $\alpha = 5\%$. The procedure requires a family of candidate dose-response models to be prespecified, that covers the range of plausible and diverse dose-response profiles.

The candidate models that best describe the expected decreasing dose-response profile of the TC groups compared to placebo include a linear model, a maximum effect (E_{\max}) model, and a sigmoid E_{\max} model. The contrasts (i.e., linear combinations of the treatment group means through the Day 29 Visit) selected to perform the MCP and that capture the shape of these candidate models are described in Table 12-1.

Table 12-1 Contrast Coefficients for the Multiple Comparisons Procedure in Part 1

Candidate Model	Placebo	TC-low	TC-mid	TC-high
Linear	3.0	1.0	-1.0	-3.0
E_{\max}	3.0	-1.0	-1.0	-1.0
Sigmoid E_{\max}	1.0	1.0	-1.0	-1.0

E_{\max} : maximum effect; TC: triple combination

A total sample size of 54 subjects in Part 1 will provide at least 90% power to detect a dose-response trend with MCP.

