- Part 1 and Part 3: Heterozygous for *F508del* with a second *CFTR* allele carrying an MF mutation that is not expected to respond to TEZ, IVA, or TEZ/IVA (Appendix A)
 - Part 2: Homozygous for *F508del*
7. FEV₁ value $\geq 40\%$ and $\leq 90\%$ of predicted mean for age, sex, and height (equations of the Global Lung Function Initiative [GLI])¹² at the Screening Visit. Spirometry measurements must meet American Thoracic Society/European Respiratory Society criteria¹³ for acceptability and repeatability.
8. Stable CF disease as judged by the investigator.
9. Willing to remain on a stable CF treatment regimen through the planned end of treatment or, if applicable, the Safety Follow-up Visit.

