9 STUDY IMPLEMENTATION

9.1 Study Design

This is a Phase 2, randomized, double-blind, placebo- and TEZ/IVA-controlled, parallel-group, 3-part, multicenter study. All parts will be conducted concurrently. Subjects may not participate in more than 1 part.

Key study elements of each part are summarized in Table 9-1, treatment arms and planned doses are shown in Table 9-2, and a schematic of the study design is shown in Figure 9-1. Study visits and assessments are shown in Table 3-1 (Part 1), Table 3-2 (Part 2), and Table 3-3 (Part 3).

Table 9-1 Key Study Elements by Part

Element	Part 1	Part 2	Part 3 (optional)
Study population			
Genotype(s)	F/MF	F/F	F/MF
Age	≥18 years	≥18 years	≥18 years
ppFEV ₁ criteria	≥40 to ≤90	≥40 to ≤90	≥40 to ≤90
Number of subjects	Approximately 54	Approximately 27	Approximately 24
Randomization			
Ratio	1:1:2:2 (placebo:TC-low:TC-mid:TC-high)	1:2 (TEZ/IVA:TC-high)	1:3 (placebo:TC2-high)
Stratification	ppFEV ₁ (<70, ≥70)	ppFEV ₁ (<70, ≥70)	ppFEV ₁ (<70, ≥70)
Study design	Parallel group	Parallel group	Parallel group
Control	Placebo	TEZ/IVA	Placebo

F/F: homozygous for *F508del*; F/MF: heterozygous for *F508del* and a minimal *CFTR* function mutation that is not expected to respond to TEZ, IVA, or TEZ/IVA; IVA: ivacaftor; ppFEV₁: percent predicted forced expiratory volume in 1 second; TC: triple combination; TEZ: tezacaftor

Table 9-2 Treatment Arms and Planned Doses by Part

	Period 1			Period 2	
	VX-659 Dosage	TEZ Dosage	IVA Dosage	TEZ Dosage	IVA Dosage
Part 1					
TC-high	400 mg qd	100 mg qd	150 mg q12h	100 mg qd	150 mg q12h
TC-mid	240 mg qd	100 mg qd	150 mg q12h	100 mg qd	150 mg q12h
TC-low	80 mg qd	100 mg qd	150 mg q12h	100 mg qd	150 mg q12h
Triple placebo	Placebo	Placebo	Placebo	Placebo	Placebo
Part 2^a					
TEZ/IVA	Placebo	100 mg qd	150 mg q12h	100 mg qd	150 mg q12h
TC-high	400 mg qd	100 mg qd	150 mg q12h	100 mg qd	150 mg q12h

Part 3 (optional)

[figure not shown]
	VX-659 Dosage	Period 1 TEZ Dosage	VX-561 Dosage
TC2-high	400 mg qd	100 mg qd	200 mg qd
Triple placebo	Placebo	Placebo	Placebo

IVA: ivacaftor; q12h: every 12 hours; qd: daily; TC: triple combination; TEZ: tezacaftor

[figure not shown]
^a In Part 2, all subjects will also receive TEZ 100 mg qd/IVA 150 mg q12h during the Run-in Period

Figure 9-1 Schematic of Study Design

[figure not shown]
Part 1: Subjects With F/MF Genotypes

Part 2: Subjects With F/F Genotype

Part 3: Subjects with F/MF Genotypes (optional)

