9.3 Rationale for Study Design and Study Drug Regimens

9.3.1 Study Design

Stratification of Randomization

The extent of response to CFTR modulator treatment may depend on the subject's ppFEV₁ value (an index of disease severity) before the start of study drug dosing. Therefore, randomization in all parts will be stratified by pretreatment ppFEV₁ values, defined as the last ppFEV₁ measurement before treatment with VX-659. For Parts 1 and 3, this value is determined at screening, except for those subjects who require a Stratification Visit, in which case the value is determined at that visit. For Part 2, the pretreatment ppFEV₁ value is determined at the Day -14 Visit during the Run-In Period.

Control Treatments

Part 1 and Part 3: Efficacy has not been demonstrated for a corrector, potentiator, or any corrector/potentiator combination in subjects with F/MF genotypes. A Phase 3 study of TEZ/IVA in subjects with F/MF genotypes (Study VX14-661-107) was terminated following a planned interim futility analysis, which showed that the combination of TEZ/IVA did not result in a prespecified improvement in ppFEV₁. Because there is no effective treatment for this population, a placebo arm will be included as the control in Part 1 and Part 3.

Part 2: A Phase 3 study of TEZ/IVA (Study VX14-661-106) demonstrated a clinically meaningful benefit in subjects with the F/F genotype¹⁶; therefore, TEZ/IVA is the active control.

Run-in Period

Part 2 will have a 4-week run-in period to establish a reliable on-treatment (TEZ/IVA) baseline for comparison to Period 1, when subjects will additionally receive VX-659 or placebo.

Period 2

Part 1 and Part 2 include a second dosing period (Period 2), during which subjects will be administered TEZ/IVA. In Part 1, Period 2 is 4 days and is included to enable a more thorough evaluation of VX-659 exposure-response relationships by conducting PK and PD assessments during the VX-659 washout. In Part 2, Period 2 is 4 weeks to enable an assessment of PD and efficacy endpoints after VX-659 is washed out.

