10.7.1 Blinding

All subjects, site personnel (including the investigator, the site monitor, and the study team), and the Vertex study team will be blinded to the treatment codes with the exception of the following:

- Any site personnel for whom this information is important to ensure the safety of the subject in the event of a life-threatening medical emergency
- Any site personnel for whom this information is important to ensure the safety of the subject and her fetus in the event of a pregnancy
- Vertex Global Patient Safety (GPS) and Regulatory Affairs personnel to satisfy serious adverse event (SAE) processing and reporting regulations
- Unblinded statistician preparing the final (production) randomization list who is not part of the study team
- Vertex IWRS Manager
- Vertex Clinical Supply Chain
- IDMC
- Vendor performing the interim analyses (IAs) and preparing the unblinded analysis for the ongoing reviews of efficacy and safety data, and the IDMC
- Bioanalytical contract research organization (CRO) analyzing PK samples and Vertex Bioanalytical personnel who are not members of the study team may review raw data from Bioanalytical CRO.
- Vertex Modeling and Simulation personnel or vendor conducting the population PK and PK/PD analyses
- Vertex medical monitor may, for matters relating to safety concerns, unblind individual subjects at any time

Blinding of Sweat Chloride and Spirometry Results:

- The Vertex study team will not have access to sweat chloride or spirometry results after a subject receives the first dose of study drug on the Day 1 Visit until after the data are unblinded for full review per Section 12.3.6.1.
- Sites, subjects, and their parents/caregivers/companions should not be informed of a subject's study-related sweat chloride results until after the subject's last study visit, even if the subject prematurely discontinues treatment.
- Subjects and their parents/caregivers/companions should not be informed of the subject's study-related spirometry results until after the subject's last study visit, even if the subject prematurely discontinues treatment.

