8.3.5 Pharmacodynamic Analysis

The sweat chloride measurement for a given visit will be calculated as the mean of the non-missing sweat chloride measurements obtained on the left and right arms at that visit. If one of the two arm measurements at a time point is missing, the other will be used as the mean. A volume ≥ 15 μL is required for an accurate determination of sweat chloride. Any results reported as having volume < 15 μL will be considered missing. Any sweat chloride values reported as < 10 mmol/L or > 160 mmol/L will be considered missing.

The analysis of the PD effect of VX-659 in combination with TEZ and either IVA or VX-561 in Parts 1, 2, and 3 on sweat chloride concentrations will be described in this section.

Descriptive analyses of the change from baseline will also be performed for all treatment groups by post-baseline visit.

8.3.5.1 Primary Analysis of the Dose Response trend of absolute change in sweat chloride from baseline through the Day 29 Visit (Part 1)

The null hypothesis to be tested is that the dose response of the mean absolute change from baseline through the Day 29 Visit for sweat chloride is not decreasing between placebo and the 3 dose levels of VX-659 with TEZ/IVA in Part 1. The test will be performed using the MCP procedure with the pre-specified contrasts provided in Section 6.2.2, within a linear MMRM framework using PROC GLIMMIX in SAS. The model will include treatment group, visit, and treatment-by-visit interaction as fixed effects and subject as a random effect, with continuous baseline ppFEV₁ and continuous baseline sweat chloride as covariates, and will include all data from all treatment groups and visits through the Day 29 Visit for analysis. The dose response test will be based on the 1-sided maximum *t*-statistic of the individual *t*-statistics for the multiple pre-specified contrasts at alpha = 5%, based on the treatment group means through the Day 29 Visit, using an unstructured covariance structure for the within-subject errors. If the model estimation does not converge, a reduced compound symmetry covariance structure will be used instead.

The tabular presentation of results for the average treatment effect across visits will be similar to the primary analysis of the primary efficacy variable for all parts. The corresponding *p*-value for the decreasing dose response trend will be provided.

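### Does testing the Part 1 sweat-chloride trend against triple placebo mislabel a TC-versus-placebo difference as a VX-659 dose response?

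*Protocol*

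**What the plan says.** Protocol 12.1.2 states that in Part 1 "a test for a decreasing dose-response trend between placebo and the TC dose groups will be performed using a multiple comparisons procedure". The statistic is the largest of three one-sided t-statistics, at alpha 5%. Table 12-1 gives the coefficients in the order placebo, TC-low, TC-mid, TC-high:

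- linear: 3, 1, −1, −3
- Emax: 3, −1, −1, −1
- sigmoid Emax: 1, 1, −1, −1

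The same section introduces these models as describing the profile of the TC groups relative to placebo.

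SAP 8.3.5.1 sets the null as a mean dose response that "is not decreasing between placebo and the 3 dose levels of VX-659 with TEZ/IVA in Part 1", and says that the p-value "for the decreasing dose response trend will be provided".

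The control arm receives placebo for all three drugs, while every TC arm receives the same TEZ/IVA (Protocol Table 9-2). Part 1 subjects need a second CFTR "allele carrying an MF mutation that is not expected to respond to TEZ, IVA, or TEZ/IVA" (Protocol 8.1).

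Three other planned pieces of evidence bear on VX-659 itself:

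- Protocol 12.3.4 and the synopsis plan all between-group sweat-chloride comparisons in an MMRM with 95% intervals. SAP 8.3.5.2 follows the primary-analysis model, whose text (SAP 8.3.1.1.1) covers all between-treatment comparisons with p-values.
- Part 1 Period 2 "is included to enable a more thorough evaluation of VX-659 exposure-response relationships by conducting PK and PD assessments during the VX-659 washout" (Protocol 9.3.1), with the TC arms still on TEZ/IVA.
- Protocol 9.3.2 says the dose range is meant to support exposure-response analyses, and Protocol 10.7.1 lists "Vertex Modeling and Simulation personnel or vendor conducting the population PK and PK/PD analyses" among those with access to treatment codes.

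**The concern.** A reader who sees a p-value for a decreasing dose response may take it to show that 400 mg does more than 80 mg. The test cannot show that by itself. Placebo has a positive coefficient in every contrast, and the Emax row weights the three TC arms equally, so a single step from placebo to any TC dose is enough to reject.

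That step is also a step in the whole regimen, because triple placebo lacks TEZ/IVA as well as VX-659. F/MF subjects are not expected to respond to TEZ/IVA. The supporting trial, however, was stopped at a futility analysis "which showed that the combination of TEZ/IVA did not result in a prespecified improvement in" ppFEV₁, which does not rule out an effect on sweat chloride.

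At stake is whether the report could present a VX-659 dose finding when only TC versus placebo had been shown. Protocol 9.3.2 adds weight, since it expects dose- and exposure-response information from Part 1 to apply to other F508del populations.

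**Working it through.** **Inputs.** Part 1 has 54 subjects randomised 1:1:2:2 (Protocol Table 9-1), giving n = 9, 9, 18, 18 for placebo, low, mid, high. Contrasts are from Table 12-1; the test is one-sided at 5%. The documents give no sweat-chloride SD, effect or dropout rate. Assumed: effects in SD units of the average change through Day 29, no missing data, 48 degrees of freedom (54 − 4 groups − 2 covariates).

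**The plan's own figure.** The stated power of at least 90% can be neither reproduced nor refuted without an effect size. Solved backwards (with 50 degrees of freedom, ignoring covariates), 90% power needs a maximum effect against placebo of 1.16 SD (TC arms equal), 1.21 SD (linear in mg), 1.23 SD (linear in dose order) or 0.93 SD (sigmoid).

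**Is the test valid?** In SD units each contrast has standard error √Σ(c²/n):

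- linear: √(9/9 + 1/9 + 1/18 + 9/18) = 1.291
- Emax: √(9/9 + 1/9 + 1/18 + 1/18) = 1.106
- sigmoid: √(1/9 + 1/9 + 1/18 + 1/18) = 0.577

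The simulated 5% critical value of the maximum t is about 2.01. With no difference between arms the rejection rate is 5.0%. The test does what it states.

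**Equal TC arms.** At 1 SD below placebo the noncentralities are 3/1.291 = 2.32, 3/1.106 = 2.71 and 1/0.577 = 1.73. Simulated rejection rates:

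| TC arms below placebo | MCP rejects |
|---|---|
| 0.25 SD | 15% |
| 0.5 SD | 34% |
| 0.75 SD | 59% |
| 1.0 SD | 81% |

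These are not false positives under the stated null. A flat TC profile below placebo is exactly the shape of the Emax row, so the table shows power against a declared alternative.

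**What a rejection means.** It does not reduce to TC versus triple placebo either, because the sigmoid row pools placebo with TC-low.

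- TC-low equal to placebo, TC-mid and TC-high 1 SD lower: noncentralities 4/1.291 = 3.10, 2/1.106 = 1.81 and 2/0.577 = 3.46. The MCP rejects in 94% of trials, and the sigmoid contrast is the largest in 79% of those. Here the signal is a change within 80 to 400 mg.
- TC-low 1 SD worse than the other three arms, which are equal: the sigmoid noncentrality is 1/0.577 = 1.73. The MCP rejects in 40%, although no TC arm beats placebo.

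A caveat saying that rejection supports TC over triple placebo would therefore be inaccurate.

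**Would a TC-only contrast add anything?** The dose-linear optimum uses n(d − d̄), with d̄ = (9×80 + 18×240 + 18×400)/45 = 272 mg. This gives weights 0.75, 0.25, −1.00 for low, mid, high and a standard error of √(0.5625/9 + 0.0625/18 + 1/18) = 0.349. TC-high minus TC-low, already planned, has √(1/9 + 1/18) = 0.408 and a 95% half-width of about 0.82 SD. Power at one-sided 5%, for 1 SD at 400 mg:

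| Shape | TC-only contrast | TC-high v TC-low |
|---|---|---|
| Linear in mg | 63% | 61% |
| Emax, ED50 40 mg | 15% | 16% |
| Emax, ED50 80 mg | 23% | 25% |
| Emax, ED50 160 mg | 34% | 36% |
| Sigmoid (low = placebo, mid = high) | 68% | 78% |

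The extra contrast gains 2 points in one shape and loses in the other four.

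**The case for a change.** The strongest case accepts that the test is valid and objects to the label. With equal TC arms 1 SD below placebo, a TC-only contrast is also significant in only 6% of the trials in which the MCP rejects. If the effect weakens with dose (relative effects 1, 0.8, 0.6 from low to high), the MCP still rejects in 58%, 89% or 99% of trials at a TC-low effect of 1, 1.5 or 2 SD. A p-value described as a decreasing dose response can thus be significant while the ordering among TC arms is reversed. TC-high versus TC-low is one of many unadjusted comparisons, with no stated role in reading the MCP.

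These figures are right, and one part stands: a rejection alone says nothing definite about ordering among the TC arms. But the plan does not say otherwise. SAP 8.3.5.1 gives the null, placebo included, in the same subsection as the p-value, and the arm means and pairwise differences that would expose a flat or reversed profile are planned outputs. No dose-selection or go/no-go rule in the public text depends on this test. The point about the missing TEZ/IVA background is softened by the expected non-response and by the Period 2 washout. The PK/PD section of the protocol and entries in the SAP contents next to the sweat-chloride analysis are redacted, so the absence of a within-TC analysis cannot be asserted with confidence.

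**Conclusion.** The concern does not hold. The MCP tests a null stated plainly to include placebo and keeps its 5% level. Its high rejection rate with equal TC arms (81% at 1 SD) is power against a shape the plan lists in advance. Following the plan as written produces no wrong result. The within-TC question is served by the planned TC-high minus TC-low estimate, the washout data and the exposure-response work; a further contrast would not improve on that pairwise comparison overall.

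The rejection rates and powers rest on assumed standardised effects, no missing data and 48 degrees of freedom. The conclusion does not depend on them: it follows from the stated null, the Table 12-1 coefficients and the comparisons already planned. What remains is ordinary care in reporting: read the trend p-value together with the arm means.

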12.2 Analysis Sets

The following analysis sets are defined: All Subjects Set, Full Analysis Set (FAS), and Safety Set. An additional analysis set related to the Run-in Period in Part 2 will be defined in the statistical analysis plan (SAP), as appropriate.

The **All Subjects Set** will include all subjects who were randomized **or** received at least 1 dose of study drug. This analysis set will be used for all individual subject data listings and disposition summary tables, unless otherwise specified.

The **FAS** will include all randomized subjects who carry the intended CFTR allele mutation **and** received at least 1 dose of study drug in Period 1. The FAS will be used to summarize subject demographics and baseline characteristics, and for all PD and efficacy analyses, unless otherwise specified. Subjects will be analyzed according to the treatment to which they were randomized.

The **Safety Set** will include all subjects who received at least 1 dose of study drug. The Safety Set will be used for all safety analyses, unless otherwise specified. Subjects will be analyzed according to the treatment they received. If a subject received at least 1 dose of a higher dose TC treatment, the subject will be analyzed in the higher dose TC treatment group. For the purpose of analysis, the priority order of increasing study drug treatment will be defined as placebo, TC-low, TC-mid, and TC-high.

12.3 Statistical Analysis

This section presents a summary of the planned statistical analyses of the PD, efficacy, and safety endpoints of the study. Statistical analysis details will be provided in the SAP.

12.3.1 General Considerations

Continuous variables will be summarized using the following descriptive summary statistics: the number of subjects (n), mean, SD, SE, median, minimum value, and maximum value. The precision of the measurement for each continuous variable will be specified in the SAP. Unless otherwise specified, minimum and maximum values will be reported with the same precision as the units of the raw data. The mean, median, SD, and SE will be reported to 1 additional decimal place. Any values that require a transformation to standard units (metric or International System [SI]) will be converted with the appropriate precision.

Categorical variables will be summarized using counts and percentages. Percentages will be presented to 1 decimal place.

The **baseline** value, unless otherwise specified, will be defined as the most recent non-missing measurement (scheduled or unscheduled) collected before the first dose of study drug in the Treatment Period (i.e., the Day 1 Visit). For ECG, baseline will be defined as the most recent pretreatment measurement (or the average of triplicate measurements, if the most recent pretreatment measurement is obtained in triplicate) before the first dose of study drug in Period 1 (i.e., the Day 1 visit).

Absolute change from baseline will be calculated as postbaseline value – baseline value.

Relative change from baseline will be calculated as (postbaseline value – baseline value)/baseline value.

The Treatment-emergent (TE) Period will include the time from the first dose in Period 1 to the Safety Follow-up Visit or 28 days after the last dose of the study drug for subjects who do not complete the Safety Follow-up Visit. Only data collected up to the end of study for a subject will be included in the analysis. An additional TE period related to the Run-in Period for Part 2 will be defined in the SAP, as appropriate.

There will be no multiplicity adjustment for performing multiple hypothesis tests.

The rules for handling missing data due to treatment or study discontinuation will be described in the SAP.

All data will be summarized for each part, separately, unless specified otherwise.

12.3.2 Background Characteristics

12.3.2.1 Subject Disposition

The number and percentage of subjects in each disposition category (e.g., randomized, included in the FAS, included in the Safety Set, completed Treatment Period, completed study/Safety Follow-up Visit, and discontinued treatment or study with a breakdown of the reasons for discontinuation) will be summarized overall and by treatment group.

12.3.2.2 Demographics and Baseline Characteristics

Demographic, background (e.g., medical history), and baseline characteristics will be summarized using descriptive summary statistics.

The following demographics and baseline characteristics will be summarized overall and by treatment group for the FAS and will include (but are not limited to): sex, race, age, weight, height, body mass index, ppFEV₁, and sweat chloride.

No statistical tests will be performed to evaluate baseline imbalance between treatment groups.

